5.4.1.1.6. Treatment Failure

A participant will be defined as on-treatment failure if he/she didn't have a reduction from baseline of at least $2 \log_{10}$ IU/mL in HBsAg levels at Week 24.

5.4.1.1.7. HBsAg Seroconversion

Seroconversion of HBsAg is defined as having achieved HBsAg seroclearance and appearance of anti-HBs antibodies.

The seroconversion will only be assessed at the time points when the anti-HBs antibodies assessment is available.

Appearance of anti-HBs antibodies is defined as a baseline anti-HBs antibodies (quantitative) <LLOQ and a post-baseline assessment \geq LLOQ. An additional seroconversion will be applied using the threshold of 10 mIU/mL, i.e. appearance of anti-HBs antibodies is defined as a baseline anti-HBs antibodies (quantitative) <10 mIU/mL and a post-baseline assessment \geq 10 mIU/mL.

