HLA	human leukocyte antigen
IA	interim analysis
IB	Investigator's Brochure
ICF	informed consent form
ICS	intracellular cytokine staining
IFLEP	Independent Flare Expert Panel
IFN(- α/γ)	(alpha/gamma) interferon
IgG	immunoglobulin G
IgM	immunoglobulin M
IL	interleukin
INR	International Normalized Ratio
ISA	intervention-specific appendix
ISR	injection site reaction
ITT	intent-to-treat
LLN	lower limit of normal
LLOQ	lower limit of quantification
MDSC	myeloid-derived suppressor cell
MoA	mode of action
MRI	magnetic resonance imaging
NA	nucleos(t)ide analog
NK	natural killer
NOAEL	no observed adverse effect level
PBMC	peripheral blood mononuclear cell
PD	pharmacodynamic(s)
PegIFN- α 2a	pegylated interferon alpha-2a
pgRNA	pre-genomic ribonucleic acid
PK	pharmacokinetic(s)
PoC	proof of concept
Q4W	every 4 weeks
QD	once daily
QTcF	QT interval corrected for heart rate according to Fridericia's formula
RBC	red blood cell
rcDNA	relaxed circular deoxyribonucleic acid
RNAi	ribonucleic acid interference
SAE	serious adverse event
SAP	Statistical Analysis Plan
SD	standard deviation
SDM	site-directed mutant
SE	standard error
siRNA	small interfering ribonucleic acid
$t_{1/2\text{term}}$	terminal half-life
T4	thyroxine
TAF	tenofovir alafenamide
TEAE	treatment-emergent adverse event
t_{max}	time to reach C_{max}
TND	target not detected
TNF	tumor necrosis factor
TSH	thyroid stimulating hormone
WBC	white blood cell

Definitions of Terms

ALT/AST nadir	Lowest ALT/AST value during study participation
End of study intervention (EOSI)	Time of the last administration of study intervention
HBsAg or HBeAg seroclearance	HBsAg or HBeAg negativity, respectively, based on the assay used
HBsAg or HBeAg seroconversion	HBsAg or HBeAg negativity and anti-HBs or anti-HBe antibody positivity, respectively
IC ₅₀	half maximal inhibitory concentration
Study intervention	As of Protocol Amendment 3: JNJ-73763989 (JNJ-3989), NA (either ETV, tenofovir disoproxil, or TAF), and PegIFN- α 2a (in Treatment Period 2)
Virologic breakthrough	Confirmed on-treatment HBV DNA increase by $>1 \log_{10}$ IU/mL from nadir or confirmed on-treatment HBV DNA level >200 IU/mL in participants who had HBV DNA level $<$ LLOQ of the HBV DNA assay

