5.4.1.1.9. HBeAg Seroconversion

Seroconversion of HBeAg is defined as having achieved HBeAg seroclearance together with appearance of anti-HBe antibodies.

Seroclearance of HBeAg is defined as (quantitative) HBeAg <LLOQ. Appearance of anti-HBe antibodies is defined as a baseline anti-HBe antibodies (qualitative) with a "NEGATIVE" result and a post-baseline assessment with "POSITIVE" result.

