5.4.2.1.8. HBeAg Seroconversion

The count and proportion of participants (and associated 90% CI) who achieve HBeAg seroconversion will be summarized by analysis phase. Separate tabulations will be made for the subset of participants who were HBeAg positive at baseline and for the subset of participants who were anti-HBe negative at baseline, respectively. The seroconversion will only be assessed at the time points when the anti-HBe antibodies assessment is available.

In addition, the count and proportion of participants (and associated 90% CI) with HBeAg seroclearance and without appearance of anti-HBe antibodies will also be summarized by analysis phase.

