5.5.2.2.3. Anti-HBs Antibodies

The actual values of and changes from baseline in anti-HBs antibodies will be summarized only descriptively in a similar manner as described for values and changes from baseline over time in other blood disease markers in Section 5.4.2.2.1.

For all participants with positive anti-HBs antibodies at baseline who will reach HBsAg seroclearance (as defined in Section 5.4.1.1.4), descriptive statistics will be calculated for the change of anti-HBs antibodies level from baseline at the timepoint when achieving the HBsAg seroclearance. In an additional summary, the change of anti-HBs antibodies level from baseline

at the specific timepoint will be summarized descriptively for the subset of the participants achieving HBsAg seroclearance at any time before or at that given timepoint if there is at least 10% of the participants for the subset.

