6.2. Appendix 2 Changes to Protocol-Planned Analyses

There are no changes to the protocol-planned analyses.

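### The SAP counts seroconversion only when antibody emerges from a negative baseline; the protocol asks only for antigen negativity with antibody positivity, and the change is not declared

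*SAP*

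**What the plan says.** Protocol Appendix 1, Definitions of Terms, defines HBsAg or HBeAg seroconversion as "HBsAg or HBeAg negativity and anti-HBs or anti-HBe antibody positivity, respectively". It sets no condition on baseline antibody. Both documents list the seroconversion proportion and the time to seroconversion as secondary endpoints.

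SAP 5.4.1.1.7 reads: "Seroconversion of HBsAg is defined as having achieved HBsAg seroclearance and appearance of anti-HBs antibodies". It then explains the second part: "Appearance of anti-HBs antibodies is defined as a baseline anti-HBs antibodies (quantitative) <LLOQ and a post-baseline assessment" at or above the LLOQ, which SAP Table 5 sets at 5 mIU/mL. A second version follows: "An additional seroconversion will be applied using the threshold of 10 mIU/mL", meaning below 10 at baseline and 10 or more later.

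SAP 5.4.1.1.9 uses the same construction for HBeAg: "Appearance of anti-HBe antibodies is defined as a baseline anti-HBe antibodies (qualitative) with a" negative result, followed by a positive one. Sections 5.4.1.3.2 and 5.4.1.3.4 carry the appearance requirement into the time-to-event endpoints.

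SAP 5.4.2 analyses all secondary endpoints in the FAS on observed cases. SAP Appendix 2 states: "There are no changes to the protocol-planned analyses".

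**The concern.** Positivity is a state at a visit; appearance is a change from baseline. The two differ for a participant who enters with antibody and then loses antigen. The protocol calls that participant a seroconverter. Under the SAP rule for that cut-off the participant counts as a non-event in the proportion, and in the time-to-event analysis is censored at the last antibody assessment without being able to have the event.

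The SAP expects such participants. Table 12 tabulates baseline anti-HBs and anti-HBe status as positive or negative, and 5.5.2.2.3 plans a summary "For all participants with positive anti-HBs antibodies at baseline who will reach HBsAg seroclearance". It also sees the denominator problem in one place: time to appearance of anti-HBe (5.5.1.3.4) is limited to anti-HBe-negative participants. Time to HBeAg seroconversion uses the same appearance rule but is limited only to HBeAg-positive participants. HBsAg seroconversion has no baseline-antibody limit at all.

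At stake is a secondary endpoint reported under the protocol's name but with a narrower definition.

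**Working it through.** **1. The plan's own figure.** The two-sided 90% Clopper-Pearson limits are the 0.05 quantile of Beta(x, n−x+1) and the 0.95 quantile of Beta(x+1, n−x). For x = 25, n = 50 this gives 0.376 to 0.624, width 0.248, as in SAP section 3. All eight intervals in SAP Table 1 reproduce to three decimals. They are not in dispute; this only fixes the interval method used in step 4.

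**2. The two rules.** Let C be antigen cleared at the visit, A0 the baseline antibody, At the antibody at that visit, and k the cut-off.

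- Protocol: C and At ≥ k.
- SAP: C and A0 < k and At ≥ k.

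The protocol gives no numeric cut-off for anti-HBs positivity, so both SAP cut-offs (5 and 10 mIU/mL) are used. For participants who clear HBsAg:

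| Baseline anti-HBs | Later anti-HBs | Protocol, k = 5 | SAP main rule | Protocol, k = 10 | SAP 10 mIU/mL rule |
|---|---|---|---|---|---|
| 2.5 | 50 | yes | yes | yes | yes |
| 7 | 7 | yes | no | no | no |
| 7 | 50 | yes | no | yes | yes |
| 50 | 7 | yes | no | no | no |
| 50 | 50 | yes | no | yes | no |

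For HBeAg, a participant anti-HBe positive at baseline who clears HBeAg and remains anti-HBe positive is a converter under the protocol and not under the SAP.

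**3. Direction.** At a given cut-off, every SAP converter is also a protocol converter, but not the reverse. With the same denominator, the SAP proportion is lower than or equal to the protocol proportion. In the Kaplan-Meier analysis, the SAP rule removes events and leaves those participants at risk for longer, so the cumulative incidence is also lower or equal.

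**4. Size, as illustration only.** The documents give neither a baseline antibody prevalence nor an expected seroconversion rate, so the converter counts below are assumed. The denominators are the planned 50 and about 20 HBeAg-positive participants (40% × 50). Observed-case denominators may be smaller. Let m be the number of converters who had antibody at baseline.

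| Endpoint | m | Converters counted | Proportion | 90% CI |
|---|---|---|---|---|
| HBsAg, protocol rule | – | 5/50 | 10% | 0.040–0.199 |
| HBsAg, SAP rule | 1 | 4/50 | 8% | 0.028–0.174 |
| HBsAg, SAP rule | 2 | 3/50 | 6% | 0.017–0.148 |
| HBsAg, SAP rule | 3 | 2/50 | 4% | 0.007–0.121 |
| HBeAg, protocol rule | – | 6/20 | 30% | 0.140–0.508 |
| HBeAg, SAP rule | 1 | 5/20 | 25% | 0.104–0.456 |
| HBeAg, SAP rule | 2 | 4/20 | 20% | 0.071–0.401 |
| HBeAg, SAP rule | 3 | 3/20 | 15% | 0.042–0.344 |

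Each uncounted converter costs 1/50 = 2 percentage points for HBsAg and 1/20 = 5 for HBeAg. With m = 0 the two rules agree.

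**The case against.** **Requiring appearance is a defensible choice.** Under the protocol wording, a participant with the same antibody level before and after treatment becomes a seroconverter through antigen loss alone, so antibody present at entry is part of the reported outcome. That stands, and it is a good reason to report both versions. It does not excuse an undeclared switch or a denominator that does not match. Protocol section 9 leaves technical detail to the SAP, but this is a term the protocol itself defines.

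**The SAP partly covers HBeAg already.** Section 5.4.2.1.8 plans a separate table in participants anti-HBe negative at baseline, which has the matched denominator. That stands for the HBeAg proportion. Nothing equivalent exists for HBsAg seroconversion or for time to seroconversion of either antigen.

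**These participants are not lost.** They still count for seroclearance and functional cure, neither of which needs antibody. That stands and limits the scope.

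**Stronger readings.** A reader might infer that anyone with detectable anti-HBs at baseline can never be a seroconverter. That goes too far: with a baseline of 5 to below 10 mIU/mL the main rule fails, but the additional 10 mIU/mL rule can still be met.

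A reader might also infer that the summary of participants "with HBeAg seroclearance and without appearance of anti-HBe antibodies" admits people who were HBeAg-negative at entry, since that sentence repeats no restriction. The SAP as a whole does not support this. Footnote a to the objectives table limits HBeAg endpoints to HBeAg-positive participants, as do 5.4.1.1.8, 5.4.1.3.3 and 5.4.1.3.4. The version-history rationale for 5.4.2.1.8 says the same. The missing words are a drafting point.

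**Conclusion.** The conflict holds for both antigens. The SAP narrows a protocol-defined secondary endpoint, keeps participants who cannot meet the narrower rule in the denominator or risk set, and declares no change. The seroconversion proportion and cumulative incidence are lower than or equal to their protocol-defined values.

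This rests on comparing the rules at the same antibody cut-off, with antigen and antibody judged at the same visit. The size cannot be derived from the documents. It is zero if nobody who clears antigen was antibody-positive at baseline, and the figures in the illustration rest on assumed counts. A reader might want to state a ceiling on the attainable HBeAg rate, but that needs a baseline anti-HBe prevalence, which the documents do not give.

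The study has no formal hypothesis or test, and the primary endpoint and sample size are unaffected. The correction is still worth making, because with few converters one or two reclassifications move the estimate visibly.

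**What to change.** In SAP 5.4.1.1.7, 5.4.1.1.9, 5.4.1.3.2 and 5.4.1.3.4, make the protocol definition the main analysis: antigen below LLOQ or negative, and antibody positive, at the same visit, whatever the baseline antibody. Report anti-HBs at both existing cut-offs, LLOQ and 10 mIU/mL.

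Keep the appearance version as supplementary, with the denominator and risk set limited to participants antibody-negative at baseline by the same cut-off. The HBeAg proportion table already exists in 5.4.2.1.8, so this adds the HBsAg proportion and the time-to-event versions.

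If the sponsor prefers appearance as the main definition, list it in SAP Appendix 2 as a change and apply the same matched denominators.

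As a minor wording point in 5.4.2.1.8, repeat the existing limit to HBeAg-positive participants in the sentence on seroclearance without anti-HBe appearance and for the anti-HBe-negative subset.

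The cost is SAP wording, one derivation flag and a few extra outputs. All the data are already collected.

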5.4.1.1.8. HBeAg Cut-offs

The cut-offs for HBeAg level are as follows:

- < 100 IU/mL
- < 10 IU/mL
- < 1 IU/mL
- < LLOQ (0.11 IU/mL)

Of note, seroclearance of HBeAg is defined as (quantitative) HBeAg <LLOQ.

The cut-offs for HBeAg change from baseline and RT are as follows:

- decrease by $\geq 0.3 \log_{10}$ IU/mL
- decrease by $\geq 0.5 \log_{10}$ IU/mL
- decrease by $\geq 1 \log_{10}$ IU/mL
- decrease by $\geq 2 \log_{10}$ IU/mL
- decrease by $\geq 3 \log_{10}$ IU/mL

Only HBeAg positive participants will be used for the analysis of the HBeAg cut-offs.

5.4.1.1.9. HBeAg Seroconversion

Seroconversion of HBeAg is defined as having achieved HBeAg seroclearance together with appearance of anti-HBe antibodies.

Seroclearance of HBeAg is defined as (quantitative) HBeAg <LLOQ. Appearance of anti-HBe antibodies is defined as a baseline anti-HBe antibodies (qualitative) with a "NEGATIVE" result and a post-baseline assessment with "POSITIVE" result.

5.4.1.1.10. HBV DNA Cut-offs

The cut-offs for HBV DNA are as follows:

- < LLOQ for target detected and not detected

- < LLOQ for target not detected
- < LLOQ for target detected
- <60 IU/mL
- <100 IU/mL
- <200 IU/mL
- <1000 IU/mL
- <2000 IU/mL
- <20000 IU/mL

5.4.1.1.11. Suppressed HBV DNA

HBV DNA < LLOQ (HBV DNA detectable or HBV DNA TND) will be evaluated over all time points when assessed with emphasis at FU Weeks 12, 24, 34 and 48, after stopping all study interventions at the end of treatment period 2 and without restarting NA treatment.

HBV DNA < LLOQ (HBV DNA detectable or HBV DNA TND) will also be evaluated at 12, 24, 36 and 48 weeks after stopping all study interventions (regardless when intervention was stopped) and without restarting NA treatment.

5.4.1.1.12. Thresholds on HBV DNA and HBsAg

The count and proportion of participants who meet HBsAg and HBV DNA thresholds will be assessed using the last available measurement.

5.4.1.1.13. ALT Normalization

ALT elevation at baseline is defined as $ALT \geq ULN$. A participant with ALT elevation at baseline achieves ALT normalization if his/her ALT value post-baseline is $< ULN$ at any given time point.

Participants who achieve ALT normalization on treatment and off treatment but without restarting NA treatment will be evaluated over time.

Participants who were retreated with NA and who have $ALT \geq ULN$ before NA re-treatment and reach ALT normalization after NA re-treatment during follow-up will be evaluated.

5.4.1.1.14. Partial Cure

Partial cure will be evaluated at each of the following time points separately: FU Week 12, 24, 36 and 48. A participant will be defined as having achieved partial cure if he/she has:

- Stopped all study interventions at any time, and
- had HBV DNA level $< 2,000$ IU/ml at the given week of interest, and
- had HBsAg $\geq LLOQ$ at the given week of interest, and
- not required NA re-treatment after stopping all study interventions.

Of note, HBV DNA level $< 2,000$ IU/ml may be achieved prior to the week of interest but must be observed at the given week of interest.

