5.4.1.1.4. HBsAg Seroclearance

Seroclearance of HBsAg is defined as a (quantitative) HBsAg level <LLOQ (see [Table 5](#)). HBsAg seroclearance can be observed prior to the time point assessed but must be observed at the given week of interest.

5.4.1.1.4.1. On Treatment

HBsAg seroclearance will be evaluated over time during the study intervention phase.

5.4.1.1.4.2. Off Treatment

HBsAg seroclearance will be evaluated over time at each of the FU timepoints separately, with emphasis at 12, 24, 36 and 48 weeks after stopping all study interventions at the end of treatment period 2 and without restarting NA treatment.

HBsAg seroclearance will be also evaluated when assessed at 12, 24, 36 and 48 weeks after stopping all study interventions (regardless when intervention was stopped) and without restarting NA treatment.

For the analyses of seroclearance at the time points mentioned above, participants with HBsAg seroclearance at the respective time points (and without restarting NA treatment during the interval between the time of stopping the study intervention up to the analysis time point (FU Week 12, 24, 36 and 48)) will be considered as having achieved this endpoint.

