5.4.1.1.5. Functional Cure

Functional cure will be evaluated at each of the following time points separately: FU Week 12, 24, 36 and 48. A participant will be defined as having achieved functional cure (FC) if he/she has:

- met the criteria for stopping NA treatment at Week 24, and
- had HBsAg seroclearance at the given week of interest, and
- not required NA re-treatment between FU Week 2 and the given week of interest.

It can be noted that a participant may achieve HBsAg seroclearance prior to the week of interest, but the HBsAg level <LLOQ has to be shown at the given week of interest to be counted as responder.

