5.4.2.1. Binary Endpoints

All binary endpoints defined using HBsAg values/changes from baseline (HBsAg cut-offs, HBsAg seroclearance/seroconversion, Functional Cure) will be analyzed.

For single arm point and 90% CI estimates the Clopper Pearson method will be used. For the difference between paired matched case-control binomial proportions, the McNemar test at 0.05 one-sided Type 1 error rate will be used.

Graphical displays using bar charts will show the binary endpoints over time, by subgroups of interest, or combining multiple binary endpoints together.

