5.4.2.1.13. Partial Cure

The count and proportion of participants (and associated 90% CI) who achieve partial cure during the study will be summarized descriptively at the selected FU time points.

The main analysis will be on observed cases data with no imputation of missing values.

Two sensitivity analyses will be performed.

1. Missing as non-response: If participants withdrew from the study prior to the selected FU time point or had missing HBsAg or HBV DNA values at the selected FU time point, they will be considered as non-responders.
2. LOCF: If participants withdrew from the study prior to the selected FU time point, they will be considered as non-responders. The LOCF rules to handle missing data for HBsAg and HBV DNA will be applied to selected time points as explained in Section [5.4.2.1.1](#).

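### Partial cure sets no end date for NA re-treatment, so re-treatment later in follow-up cancels partial cure at earlier weeks

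*SAP*

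**What the plan says.** SAP 5.4.1.1.14 states: "Partial cure will be evaluated at each of the following time points separately: FU Week 12, 24, 36 and 48". A participant must meet four conditions. Two of them, HBV DNA below 2,000 IU/mL and HBsAg at or above LLOQ, must hold "at the given week of interest, and" so are tied to the assessment week. The other two are not tied to it: "Stopped all study interventions at any time, and" and "not required NA re-treatment after stopping all study interventions".

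The analysis section, SAP 5.4.2.1.13, refers to participants "who achieve partial cure during the study will be summarized descriptively at the selected FU time points" and adds no time limit.

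The neighbouring endpoints do set one. Functional cure (SAP 5.4.1.1.5) requires that the participant has "not required NA re-treatment between FU Week 2 and the given week of interest". Off-treatment HBsAg seroclearance (SAP 5.4.1.1.4) requires a response "without restarting NA treatment during the interval between the time of stopping the study intervention up to the analysis time point". The additional summaries of off-treatment seroclearance (SAP 5.4.2.1.3.2) and HBV DNA suppression (SAP 5.4.2.1.10) likewise look only at NA restarts before the time point.

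**The concern.** A status assessed at a given week should depend on what is known up to that week. Without an end date, the partial-cure status at FU Week 12 can be overturned by an event at FU Week 40. Four things follow.

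- **Interim to final.** The FU Week 12 rate can drop between the FU Week 12 interim and the final analysis although no FU Week 12 measurement has changed. SAP 5.8.3.2 says the interims support health-authority interactions and decisions on further studies.
- **Length of follow-up.** A participant who leaves the study soon after FU Week 12 keeps that week's status, while one followed longer can lose it. Within one interim, participants enrolled early have had more time to lose it than those enrolled late.
- **Shape over time.** Participants who later need NA are removed from every week, so the partial-cure table shows less decline than occurred.
- **Use elsewhere.** Partial cure at FU Week 24 is a grouping variable for the HBsAg, HBeAg, HBV DNA and ALT summaries (SAP 5.4.2.2.1) and an outcome in the Table 6 correlations (SAP 5.5.1.4.1). Both inherit the look-ahead.

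**Working it through.** **1. The plan's own figure.** The documents give no planning figure for partial cure. The only one is the precision table for the primary endpoint (SAP section 3, Table 1). SAP 5.4.2.1 gives the interval method for binary endpoints: "For single arm point and 90% CI estimates the Clopper Pearson method will be used". With x responders out of n, the two-sided 90% limits are the 5th percentile of Beta(x, n−x+1) and the 95th percentile of Beta(x+1, n−x). For 25/50 this gives 0.376 to 0.624, width 0.248, as stated. All eight rows of Table 1 reproduce to three decimals. The same formula is used below.

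**2. The definitions applied to two participants.** Both meet the completion criteria at Week 24 and stop NA at FU Week 2. Both have HBV DNA below 2,000 IU/mL at FU Week 24, and both are re-treated at FU Week 40.
- Participant A has HBsAg below LLOQ at FU Week 24. The functional-cure condition ends at FU Week 24, so A keeps functional cure at that week.
- Participant B has HBsAg at or above LLOQ at FU Week 24. The partial-cure condition has no end, so B loses partial cure at FU Week 24, and at FU Weeks 12 and 36 too.

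The histories match except for HBsAg, yet the two neighbouring endpoints treat the later re-treatment differently. Their rates cannot be read side by side.

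**3. A simple count (all counts assumed).** Take N = 50. At FU Week 12, 12 participants are off NA and meet the HBV DNA and HBsAg conditions. Of these, 5 are re-treated between FU Week 12 and FU Week 48, and the other 7 keep meeting the conditions.
- With an end date: 12/50 = 24% (90% CI 14.5 to 36.0) at FU Week 12, and (12−5)/50 = 7/50 = 14% (6.8 to 24.7) at FU Week 48.
- As written, at the final analysis: 14% at both weeks. The 10-point fall is absent from the table.

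**4. A time course (all counts assumed).** Take N = 50 with 15 responders at FU Week 12 and 0, 3, 6 and 9 cumulatively re-treated by FU Weeks 12, 24, 36 and 48.

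| FU Week | With end date (90% CI) | As written (90% CI) |
|---|---|---|
| 12 | 15/50 = 30% (19.5 to 42.4) | 6/50 = 12% (5.4 to 22.3) |
| 24 | 12/50 = 24% (14.5 to 36.0) | 6/50 = 12% (5.4 to 22.3) |
| 36 | 9/50 = 18% (9.7 to 29.3) | 6/50 = 12% (5.4 to 22.3) |
| 48 | 6/50 = 12% (5.4 to 22.3) | 6/50 = 12% (5.4 to 22.3) |

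Other assumptions move the FU Week 12 gap. With 10 responders and 3 later re-treated, it is 20% versus 7/50 = 14%. With 20 responders and 16 later re-treated, it is 40% versus 4/50 = 8%.

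**5. Table 6.** A categorical outcome is evaluated only if at least 10% respond (SAP 5.5.1.4.1). Assume 7 responders at FU Week 24, with 3 re-treated later. With an end date, 7/50 = 14% and the outcome is analysed. As written, 4/50 = 8% and it is dropped.

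The denominator of 50 is a simplification throughout, since the main analysis uses observed cases only (SAP 5.4.2.1.13).

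**The case against.** **The wording may only be ambiguous.** Partial cure is assessed at each week separately, so a programmer could read the condition as running up to that week. That is fair, and it may be what was meant. But the text does not say so, its analysis section does not say so, and the SAP states the limit each time it wants it for the related endpoints. The written definition should not depend on a guess.

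**The endpoint is minor.** Partial cure is descriptive and is not named among the protocol's endpoints, and no formal testing is planned for the study (SAP 5.1.7). This stands, and it limits the weight of the point.

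A reader might also infer three stronger things, which the documents do not support.

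- *That relapse is hidden in the trial's results.* It is not. HBV DNA cut-offs, including 2,000 IU/mL, are summarised over time (SAP 5.4.2.1.9), as is NA re-treatment (5.4.2.1.2.1). Flares followed by re-treatment are reported by type (5.4.2.1.15). A rise in HBV DNA to 2,000 IU/mL or more without re-treatment still shows as a fall in partial cure. Only the partial-cure table and the analyses built on it are affected.
- *That many participants still on NA would be counted.* The stopping condition, "Stopped all study interventions at any time, and", does not say that the stop must precede the week assessed. Each participant wrongly admitted would add 1/50 = 2 percentage points. But Protocol 6.6 has NA either stopped at FU Week 2 or continued through follow-up. The documented exception is early discontinuation of the investigational treatment, after which NA may be stopped in consultation with the sponsor. The phrase may exist to include exactly those participants. Few should be affected.
- *That the FU Week 12 interim would show the full bounded rate.* SAP 5.8.3.2 allows interims to include later data from participants who have them. In the example in step 3, 24% is an upper value; the interim could show anything from 14% to 24%.

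**Conclusion.** Wrong as written. The re-treatment condition has no end date, and followed literally it makes partial cure at FU Weeks 12, 24 and 36 depend on later NA re-treatment and on length of follow-up. This rests on the wording of SAP 5.4.1.1.14 and on the contrast with 5.4.1.1.4 and 5.4.1.1.5; no other section supplies the missing limit.

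The direction is certain: under the literal rule, late re-treatment can only lower the early-week rates. The size is unknown and depends on how many early responders are re-treated later. The percentages above illustrate the mechanism and are not estimates. FU Week 48 is the last scheduled visit, so it is essentially unaffected, as are the by-group summary and Table 6 outcome at that week.

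**What to change.** In SAP 5.4.1.1.14, give the fourth condition an end: *has not required NA re-treatment from the stop of all study interventions up to the week being assessed*. Keep the idea of re-treatment being required, as functional cure does. The SAP separates meeting the re-treatment criteria from actually restarting NA and takes them from different CRF pages (5.4.1.1.2). Replacing required with received would change the endpoint.

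As a minor clarification, let the first condition say that all study interventions, NA included, were stopped at any time *before* the week being assessed. Before is safer than on or before, which would admit someone whose HBV DNA that week was measured while still on NA.

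The cost is a date comparison in the derivation. No new data are needed and no clinical rule changes. Some partial-cure figures at FU Weeks 12, 24 and 36 may change, as may the FU Week 24 by-group summary and Table 6 correlation.
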